8.1 TRIAL APPROVAL, SUBJECT INFORMATION, INFORMED CONSENT

This trial will be initiated only after all required legal documentation has been reviewed and approved by the respective Institutional Review Board (IRB) / Independent Ethics Committee (IEC) and competent authority (CA) according to national and international regulations. The same applies for the implementation of changes introduced by amendments.

Prior to a subject's participation in the trial, written informed consent must be obtained from each subject (or the subject's legally accepted representative) according to ICH-GCP and to the regulatory and legal requirements of the participating country. Each signature must be personally dated by each signatory and the informed consent and any additional subject-information form retained by the investigator as part of the trial records. A signed copy of the informed consent and any additional subject information must be given to each subject or the subject's legally accepted representative.

The subject must be given sufficient time to consider participation in the trial. The investigator or delegate obtains written consent of the subject's own free will with the informed consent form after confirming that the subject understands the contents. The investigator or delegate must sign (or place a seal on) and date the informed consent form. If a trial collaborator has given a supplementary explanation, the trial collaborator also signs (or places a seal on) and dates the informed consent.

Re-consenting may become necessary when new relevant information becomes available and should be conducted according to the sponsor's instructions.

The consent and re-consenting process should be properly documented in the source documentation.

8.2 DATA QUALITY ASSURANCE

A risk-based approach is used for trial quality management. It is initiated by the assessment of critical data and processes for trial subject protection and reliability of the results as well as identification and assessment of associated risks. An Integrated Quality and Risk Management Plan documents the rationale and strategies for risk management during trial conduct including monitoring approaches, vendor management and other processes focusing on areas of greatest risk.

Continuous risk review and assessment may lead to adjustments in trial conduct, trial design or monitoring approaches.

A quality assurance audit/inspection of this trial may be conducted by the sponsor, sponsor's designees, or by IRB / IEC or by regulatory authorities. The quality assurance auditor will have access to all medical records, the investigator's trial-related files and correspondence, and the informed consent documentation of this clinical trial.

8.3 RECORDS

CRFs for individual subjects will be provided by the sponsor. For drug accountability, refer to Section [4.1.8](#).

ClinBaseTM

In the Human Pharmacology Centre (HPC) – Boehringer Ingelheim's Phase I unit – the validated ClinBaseTM system is used for processing information and controlling data collected in clinical studies. In addition to its function as a procedure control system, ClinBaseTM serves as data base. Instead of being entered into CRFs, selected data are directly entered into the system.

8.3.1 Source documents

In accordance with regulatory requirements, the investigator should prepare and maintain adequate and accurate source documents and trial records for each trial subject that include all observations and other data pertinent to the investigation. Source data as well as reported data should follow the 'ALCOA principles' and be attributable, legible, contemporaneous, original, and accurate. Changes to the data should be traceable (audit trail).

Data reported on the CRF must be consistent with the source data or the discrepancies must be explained.

Before providing any copy of subjects' source documents to the sponsor, the investigator must ensure that all subject identifiers (e.g., subject's name, initials, address, phone number, and social security number) have properly been removed or redacted to ensure subject confidentiality.

If the subject is not compliant with the protocol, any corrective action (e.g. re-training) must be documented in the subject file.

For the CRF, data must be derived from source documents, for example:

Proprietary confidential information © 2019 Boehringer Ingelheim International GmbH or one or more of its affiliated companies

- Subject identification: sex, year of birth (in accordance with local laws and regulations)
- Subject participation in the trial (substance, trial number, subject number, date subject was informed)
- Dates of subject's visits, including dispensing of trial medication
- Medical history (including trial indication and concomitant diseases, if applicable)
- Medication history
- AEs and outcome events (onset date [mandatory], and end date [if available])
- SAEs (onset date [mandatory], and end date [if available])
- Concomitant therapy (start date, changes)
- Originals or copies of laboratory results and other imaging or testing results, with proper documented medical evaluation (in validated electronic format, if available)
- ECG results (original or copies of printouts)
- Completion of subject's participation in the trial (end date; in case of premature discontinuation, document the reason for it, if known)
- Prior to allocation of a subject to a treatment into a clinical trial, there must be documented evidence in the source data (e.g. medical records) that the trial participant meets all inclusion criteria and does not meet any exclusion criteria. The absence of records (either medical records, verbal documented feedback of the subject or testing conducted specific for a protocol) to support inclusion/exclusion criteria does not make the subject eligible for the clinical trial.

Data directly entered into ClinBaseTM (that is, without prior written or electronic record) are considered to be source data. The place where data are entered first will be defined in a trial specific Source Data Agreement. The data in ClinBaseTM are available for inspection at any time.

8.3.2 Direct access to source data and documents

The investigator /institution will allow site trial-related monitoring, audits, IRB / IEC review and regulatory inspections. Direct access must be provided to the CRF and all source documents/data, including progress notes, copies of laboratory and medical test results, which must be available at all times for review by the Clinical Research Associate, auditor and regulatory inspector (e.g. FDA). They may review all CRFs and informed consents. The accuracy of the data will be verified by direct comparison with the source documents described in section [8.3.1](#). The sponsor will also monitor compliance with the protocol and GCP.

8.3.3 Storage period of records

Trial site:

The trial site(s) must retain the source and essential documents (including ISF) according to the local requirements valid at the time of the end of the trial.

Sponsor:

The sponsor must retain the essential documents according to the sponsor's SOPs.

8.4 EXPEDITED REPORTING OF ADVERSE EVENTS

BI is responsible to fulfil their legal and regulatory reporting obligation in accordance with regulatory requirements.

8.5 STATEMENT OF CONFIDENTIALITY AND SUBJECT PRIVACY

Individual subject data obtained as a result of this trial is considered confidential and disclosure to third parties is prohibited with the exceptions noted in section [8.7](#).

Data protection and data security measures are implemented for the collection, storage and processing of patient data in accordance with the principles 6 and 12 of the WHO GCP handbook.

Personalised treatment data may be given to the subject's personal physician or to other appropriate medical personnel responsible for the subject's welfare. Data generated at the site as a result of the trial need to be available for inspection on request by the participating physicians, the sponsor's representatives, by the IRB / IEC and the regulatory authorities.

8.5.1 Collection, storage and future use of biological samples and corresponding data

Measures are in place to comply with the applicable rules for the collection, storage and future use of biological samples and clinical data, in particular

- Sample and data usage has to be in accordance with the informed consent
- The BI-internal facilities storing biological samples from clinical trial participants as well as the external banking facility are qualified for the storage of biological samples collected in clinical trials.
- An appropriate sample and data management system, incl. audit trail for clinical data and samples to identify and destroy such samples according to ICF is in place
- A fit for the purpose documentation (e.g., biomarker proposal, analysis plan and report) ensures compliant usage
- If applicable, a fit for purpose approach will be used for assay/equipment validation depending on the intended use of the biomarker data

Samples and/or data may be transferred to third parties and other countries as specified in the ICF

8.6 TRIAL MILESTONES

The **start of the trial** is defined as the date of the enrolment of the first subject in the trial.

The **end of the trial** is defined as the 'date of the last visit of the last subject in whole trial' ('Last Subject Completed') or 'end date of the last open AE' or 'date of the last follow-up test' or 'date of an AE has been decided as sufficiently followed-up', whichever is latest.

Proprietary confidential information © 2019 Boehringer Ingelheim International GmbH or one or more of its affiliated companies

Early termination of the trial is defined as the premature termination of the trial for any reason before the end of the trial as specified in this protocol.

Temporary halt of the trial is defined as any unplanned interruption of the trial by the sponsor with the intention to resume it.

Suspension of the trial is defined as an interruption of the trial based on a Health Authority request.

The EC/competent authority in each participating EU member state will be notified about the trial milestones according to the laws of each member state.

A final report of the clinical trial data will be written only after all subjects have completed the trial in all countries (EU or non-EU), so that all data can be incorporated and considered in the report.

The sponsor will submit to the EU database a summary of the final trial results within one year from the end of a clinical trial as a whole, regardless of the country of the last patient (EU or non-EU).

8.7 ADMINISTRATIVE STRUCTURE OF THE TRIAL

The trial is sponsored by Boehringer Ingelheim (BI).

The trial will be conducted at the Human Pharmacology Centre (HPC) of BI Pharma GmbH & Co. KG, Biberach, Germany, under the supervision of the Principal Investigator. Relevant documentation on the participating (Principal) Investigators (e.g. their curricula vitae) will be filed in the ISF.

BI has appointed a Clinical Trial Leader, responsible for coordinating all required trial activities, in order to

- Manage the trial in accordance with applicable regulations and internal SOPs
- Direct the clinical trial team in the preparation, conduct, and reporting of the trial
- ensure appropriate training and information of Clinical Trial Managers (CTM), Clinical Research Associates, and investigators of participating trial sites

The trial medication will be provided by the Clinical Trial Supplies Unit, BI Pharma GmbH & Co. KG, Biberach, Germany.

Safety laboratory tests will be performed by the local laboratory of the trial site ().

Analyses of BI 894416 concentrations in plasma will be performed at

On-site monitoring will be performed by BI or a contract research organisation appointed by BI.

Data management and statistical evaluation will be done by BI or a contract research organization appointed by BI according to BI SOPs.

Tasks and functions assigned in order to organise, manage, and evaluate the trial are defined according to BI SOPs. A list of responsible persons and relevant local information can be found in the ISF.

10. APPENDICES

Not applicable.

Proprietary confidential information © 2019 Boehringer Ingelheim International GmbH or one or more of its affiliated companies

11. DESCRIPTION OF GLOBAL AMENDMENT(S)

11.1 GLOBAL AMENDMENT 1

Date of amendment	19 Feb 2019
EudraCT number	2018-004313-41
EU number	
BI Trial number	1371-0021
BI Investigational Medicinal Product(s)	BI 894416
Title of protocol	Relative bioavailability of BI 894416 as tablet formulation following a high-fat, high-calorie breakfast compared to administration in the fasting state in healthy male subjects (an open-label, randomised, single-dose, two-period, two-sequence crossover study)
To be implemented only after approval of the IRB / IEC / Competent Authorities	
To be implemented immediately in order to eliminate hazard – IRB / IEC / Competent Authority to be notified of change with request for approval	
Can be implemented without IRB / IEC / Competent Authority approval as changes involve logistical or administrative aspects only	
Section to be changed	
1) Flow Chart2) 3.3.33) 3.3.4.14) 4.1.35) 5.2.36) 6.2.27) 6.2.3
Description of change	
1) Addition of safety laboratory and AE questioning within 5 days prior to administration in the first treatment period; change of post-dose ECG and VS time points post dose on Day 1 to +1:00 h and +2:00 h; addition of AE questioning on Day 1 at +1:00 h; addition of neurological examination to end-of-trial examination2) Reduction of maximum allowable alcohol consumption to 24 g/day; addition of exclusion criteria 26 and 273) Addition of treatment discontinuation criterion 64) Clarification that all subjects may be treated on the same calendar day5) Addition of safety laboratory parameter set C

Proprietary confidential information © 2019 Boehringer Ingelheim International GmbH or one or more of its affiliated companies

	
6) Adaption of treatment period 1 duration 7) Addition of neurological examination

Rationale for change	
1) In response to IEC / Competent Authority objection 2) In response to IEC / Competent Authority objection 3) In response to IEC / Competent Authority objection 4) In response to IEC / Competent Authority objection 5) To detail parameters to be measured within 5 days prior to first administration of trial drug (see point 1 above) 6) To account for addition of a safety laboratory examination prior to treatment period 1 (see point 1 above) 7) In response to IEC / Competent Authority objection

11.2 GLOBAL AMENDMENT 2

2. LIST OF ABBREVIATIONS

See Medicine Glossary:

[website: glossary](#)

Term	Definition / description
ALT	Alanine transaminase
ANOVA	Analysis of variance
AST	Aspartate transaminase
AUC _{0-tz}	Area under the concentration-time curve of the analyte in plasma over the time interval from 0 to the last quantifiable data point
AUC _{0-∞}	Area under the concentration-time curve of the analyte in plasma over the time interval from 0 extrapolated to infinity
BMI	Body mass index
BWC	Bioavailability/Bioequivalence, within-subject design, time-controlled
CI	Confidence interval
C _{max}	Maximum measured concentration of the analyte in plasma
CV	Arithmetic coefficient of variation
DBLM	Database lock meeting
DILI	Drug induced liver injury
gCV	Geometric coefficient of variation
gMean	Geometric mean
LLT	Lower level term
Max	Maximum
MedDRA	Medical Dictionary for Regulatory Activities
Min	Minimum
N	Number non-missing observations
P10	10th percentile
P90	90th percentile
PKS	PK parameter set
Q1	1st quartile
Q3	3rd quartile
R / Ref	Reference treatment
RAGe	Report Appendix Generator system

Term	Definition / description
SD	Standard deviation
SOC	System organ class
T	Test treatment
TS	Treated set
ULN	Upper limit of normal
WHO-DD	World Health Organization Drug Dictionary
XPKISTAT	Library of SAS [®] Macros for PK analysis

3. INTRODUCTION

As per ICH E9 ([1](#)), the purpose of this document is to provide a more technical and detailed elaboration of the principal features of the analysis described in the protocol, and to include detailed procedures for executing the statistical analysis of the primary and secondary variables and other data.

This Trial statistical analysis plan (TSAP) assumes familiarity with the Clinical Trial Protocol (CTP). In particular, the TSAP is based on the planned analysis specification as written in CTP Section 7 “Statistical Methods and Determination of Sample Size”. Therefore, TSAP readers may consult the CTP for more background information on the study, e.g., on study objectives, study design and population, treatments, definition of measurements and variables, planning of sample size, randomisation.

Study data (including data entered in the RAVE EDC system and external data provided by suppliers) will be stored in a Clinical Data Repository (CDR).

Pharmacokinetic (PK) parameters will be calculated using Phoenix WinNonlinTM software (version 6.3 or higher, Certara USA Inc., Princeton, NJ, USA).

The statistical analyses will be performed within the validated working environment CARE, including SASTM (current Version 9.4, by SAS Institute Inc., Cary, NC, USA), and a number of SASTM-based tools (e.g., macros for the analyses of AE data or laboratory data; Report Appendix Generator system (RAGe) for compilation/formatting of the CTR appendices).

4. CHANGES IN THE PLANNED ANALYSIS OF THE STUDY

All analyses as planned in the CTP will be performed and are described in more detail in this TSAP.

5. ENDPOINTS

5.1 PRIMARY ENDPOINTS

Section 2.1.2 of the CTP: *The following pharmacokinetic parameters will be determined for BI 894416:*

- *AUC_{0-t_z} (area under the concentration-time curve of the analyte in plasma over the time interval from 0 to the last quantifiable data point)*
- *C_{max} (maximum measured concentration of the analyte in plasma)*

5.2 SECONDARY ENDPOINTS

5.2.1 Key secondary endpoints

This section is not applicable as no key secondary endpoints have been defined in the CTP.

5.2.2 Secondary endpoints

Section 2.1.3 of the CTP: *The following pharmacokinetic parameter will be determined for BI 894416:*

- *AUC_{0-∞} (area under the concentration-time curve of the analyte in plasma over the time interval from 0 extrapolated to infinity)*

6. GENERAL ANALYSIS DEFINITIONS

6.1 TREATMENTS

For basic study information on investigational products, assignment of treatment sequences and selection of doses, please see CTP, Sections 3 and 4.

The study will be performed as a randomised, open-label, two-way crossover trial with two treatments (T and R) and two treatment sequences (TR or RT).

In total, it was planned to assign 14 healthy male subjects to the two treatment sequences in a 1:1 ratio.

For details of dosage and formulation see Table 6.1: 1 below:

Table 6.1: 1 Treatments and labels used in the analysis

Treatment	Short label	Short label for footnote
R BI 894416, 3*10 mg tablet, qd, fasted	BI 30mg fast	BI 894416 30mg fast
T BI 894416, 3*10 mg tablet, qd, fed	BI 30mg fed	BI 894416 30mg fed

The following separate study phases will be defined for the analyses of AEs:

- **Screening** (ranging from 0:00 h on day of informed consent until first administration time of study drug)
- **On treatment** (separately for each treatment; i.e. ranging from the time of administration of the respective treatment until next drug administration or 0:00 h on the day after trial termination date)

Displays of AEs will be presented separately for the treatments described in [Table 6.1: 1](#) above

Two types of AE displays will be provided in the report:

A) Section 15.3 and Appendix 16.1.13.1.8 (for ClinicalTrials.gov and EudraCT only) of the CTR displays:

In these displays, the on treatment phase will be analysed (labelled with the name of the study treatment (short label)). Screening will not be included in this analysis.

The following total will be provided in addition (Section 15.3 only):

- a total over all on treatment phases included in this analysis ("Total on treatment")

B) Section 15.4 and Appendix 16.1.13.1.8 (except for ClinicalTrials.gov and EudraCT) of the CTR displays:

- Screening
- On treatment (labelled with the name of the study treatment (short label))

In Section 16.1.13.1.8 AE tables, the following totals will be provided in addition:

- a total over all study phases ("Total")

For detailed information on the handling of the treatments refer to Technical TSAP ADS plan and Analysis Data Reviewers guide.

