4.1.4 Drug assignment and administration of doses for each subject

This trial is a 2-way crossover study. All subjects will receive the 2 treatments in randomised order. The treatments to be evaluated are outlined in Table 4.1.4: 1 below.

Table 4.1.4: 1 Dosage and treatment schedule

Treatment	Substance	Formulation	Unit strength	Dosage	Total dose
T (Test)	BI 894416	Tablet	10 mg	3 tablets (30 mg) as one single dose on Day 1 following a high-fat, high-calorie breakfast	30 mg
R (Reference)	BI 894416	Tablet	10 mg	3 tablets (30 mg) as one single dose on Day 1 in the fasting state	30 mg

Administration of investigational medicinal product: The investigator (or authorised designee) will administer the trial medication as an oral dose together with about 240 mL of water to subjects who are in a sitting/standing position. For drug administration, the so-called four-eye principle (two-person rule) should be applied. For this, one authorised employee of the trial site should witness the administration of trial medication, and – if applicable – its preparation (e.g. reconstitution), if correct dosage cannot be ensured otherwise.

Treatment R: Administration of trial medication will be performed after subjects have fasted overnight; fasting is to start no later than 10 h before the scheduled dosing.

Treatment T: Subjects are to fast overnight prior to administration. Fasting is to start no later than 10 h before the scheduled dosing. A high-fat, high-calorie meal will be served 30 min before drug administration. The subjects must completely consume the meal prior to drug intake. The composition of the standard high-fat, high-calorie meal is detailed in Table [4.1.4: 2](#); this meal is in compliance with the FDA guidance ‘Food-Effect Bioavailability and Fed Bioequivalence Studies’ [[R03-2269](#)]. For restrictions with regard to diet, see Section [4.2.2.2](#).

Proprietary confidential information © 2019 Boehringer Ingelheim International GmbH or one or more of its affiliated companies

Table 4.1.4: 2

Composition of the high-fat, high-calorie meal

Ingredients	kcal
2 chicken eggs (whole content) for scrambled eggs ¹	192
10 g butter for frying scrambled eggs	75
35 g fried bacon	186
2 toasted slices of wheat bread	130
15 g butter for buttering toast slices	113
115 g hash brown potatoes	132
240 mL whole milk (3.5% fat)	156
Sum²	984

¹ Whole eggs or liquid egg may be used

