7.3.4 Safety analyses

Safety will be analysed based on the assessments described in Section [2.2.2.2](#). All treated subjects (TS, refer to Section [7.2](#)) will be included in the safety analysis. Safety analyses will be descriptive in nature and based on BI standards. No hypothesis testing is planned.

For all analyses, the treatment actually administered (= treatment at onset) to the subject will be used (any deviations from the randomised treatment will be discussed in the minutes of the Report Planning Meeting).

Treatments under fed and under fasted condition will be compared in a descriptive way. Tabulations of frequencies/proportions will be used to evaluate categorical (qualitative) data, and tabulations of descriptive statistics will be used to analyse continuous (quantitative) data.

Measurements (such as ECG, vital signs, or laboratory parameters) or AEs will be assigned to treatments (see Section [4.1](#)) based on the actual treatment at the planned time of the measurement or on the recorded time of AE onset (concept of treatment emergent AEs).

Therefore, measurements planned or AEs recorded prior to first intake of trial medication will be assigned to the screening period and those between trial medication intake and the trial medication intake in the next treatment period or the EoTrial Visit (whatever comes next) will be assigned to the respective treatment. In case of two or more treatments, the follow-up will be summarized according to the previous treatment. These assignments including the

Proprietary confidential information © 2019 Boehringer Ingelheim International GmbH or one or more of its affiliated companies

corresponding time intervals will be defined in detail in the TSAP. Note that AEs occurring after the last per protocol contact but entered before final database lock will be reported to Pharmacovigilance only and will not be captured in the trial database.

Additionally, further treatment intervals (analysing treatments) may be defined in the TSAP in order to provide summary statistics for time intervals, such as combined treatments, on-treatment totals, or periods without treatment effects (such as screening and follow-up intervals).

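### An AE that starts during the fed-condition breakfast is never shown under fed, and in sequence R-T it is tabulated as an on-treatment AE of the fasted dose

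*SAP*

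**What the plan says.** SAP 6.1 bounds every AE phase by drug intake. Screening is "ranging from 0:00 h on day of informed consent until first administration time of study drug". Each on-treatment phase is "ranging from the time of administration of the respective treatment until next drug administration", and the last one closes at midnight after trial termination. For the CTR Section 15.3 tables and the registry displays the SAP adds "Screening will not be included in this analysis". The Section 15.4 displays do show Screening.

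Protocol 7.3.4 sets the same rule. AEs are assigned "based on the actual treatment at the planned time of the measurement or on the recorded time of AE onset", and a treatment receives "those between trial medication intake and the trial medication intake in the next treatment period or the EoTrial Visit". The same section plans a descriptive comparison of the fed and fasted conditions and lets the SAP define further intervals. SAP 6.1 defines none around dosing.

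On the meal, Protocol 4.1.4 says, for treatment T only, "A high-fat, high-calorie meal will be served 30 min before drug administration" and "The subjects must completely consume the meal prior to drug intake". The Flow Chart agrees: breakfast at -0:30, tablets at 0:00.

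SAP 7.8.1 notes that no residual effect period has been defined and treats all AEs up to the end-of-trial examination as on treatment. Nothing therefore closes the period-1 phase before the period-2 tablet.

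**The concern.** The breakfast is the only planned difference between T and R, yet it falls in the phase before T. Nausea or abdominal discomfort that starts while the subject is eating, in period 2 of sequence R-T, is entered under *BI 30mg fast*. That subject is not fasting at the time, and his fasted dose was taken at least 5 days earlier.

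At stake is the reading of the descriptive fed-versus-fasted AE tables. The meal precedes T only, so the events it provokes can be added to the fasted column or left out of the on-treatment tables, but can never be added to the fed column. The pharmacokinetic endpoints are not touched.

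**Working it through.** This is an assignment rule, so the plan gives no figure to reproduce. The check applies SAP 6.1 literally to both sequences.

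**Inputs**
- Phase boundaries: drug intakes only (SAP 6.1; Protocol 7.3.4).
- Breakfast: from -0.5 h to intake, T only (Protocol 4.1.4; Flow Chart).
- Gap between the two doses: at least 5 days, 5 × 24 = 120 h (Protocol 6.2.2).
- Subjects: 14 planned, allocated 1:1, 14/2 = 7 per sequence (SAP 6.1).
- Geometric mean half-life: 3.0 to 5.8 h (Protocol 1.2.1).

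**Rule.** With intake times d1 and d2, an AE with onset t is Screening if t < d1, belongs to the first treatment if d1 ≤ t < d2, and to the second if t ≥ d2.

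**Result by sequence**, with d1 = 0 and d2 = 120 h:

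| Onset | Sequence R-T | Sequence T-R |
|---|---|---|
| 0.50 h before T intake | R (fasted, on treatment) | Screening |
| 0.25 h before T intake | R (fasted, on treatment) | Screening |
| 0.01 h before T intake | R (fasted, on treatment) | Screening |
| At T intake or 0.25 h after | T (fed) | T (fed) |
| 0.25 h before R intake (no meal) | Screening | T (fed) |

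No breakfast-window onset reaches the fed column in either sequence.

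**Direction.** The last row shows that pre-dose events in general are carried back symmetrically: before the second dose they go to fasted in R-T and to fed in T-R. Meal-provoked events have no counterpart before R, so for them the shift is one-sided.

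**Distance from the fasted dose.** 120/5.8 = 20.7 and 120/3.0 = 40, so at least about 20 half-lives have passed when the fasted column receives the event.

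**Size.** The window is 0.5/120 = 0.42% of the shortest possible fasted phase in R-T and concerns 7 subjects. The documents give no rate for AEs at breakfast. For an assumed per-subject chance p, the expected number of R-T subjects with an event moved to fasted is 7p, and the chance of at least one is 1 - (1 - p)^7:

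| Assumed p | 7p | Chance of at least one |
|---|---|---|
| 1% | 0.07 | 6.8% |
| 5% | 0.35 | 30% |
| 10% | 0.70 | 52% |

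The expected number sent to Screening in T-R is also 7p.

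**The case against.** The strongest reply is that the SAP does what the protocol tells it to do. Protocol 7.3.4 uses the treatment-emergent concept with intake-to-intake intervals and sends anything before the first intake to screening. Its permission to define further intervals is optional. Protocol 7.1 defines T as drug administration after the meal, so the tablet is the treatment and the meal is its condition. An AE before the tablet says nothing about how the drug is tolerated with food. All of this stands, and it makes a tempting stronger reading wrong: a reader might infer that SAP and protocol conflict, or that the fed phase ought to begin at breakfast. Beginning it there would override the protocol's screening assignment in T-R and put events that precede the period's tablet into a drug column.

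Second, T-R events do not disappear. They are shown under Screening in Section 15.4, like any other pre-dose event. This also stands.

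Third, causality is judged separately with timing in view (Protocol 5.2.6.1.6), and drug-related AEs have their own table (SAP 7.8.1). A breakfast event some 20 half-lives after the fasted dose is unlikely to be called related. This protects the drug-related table but not the table of all AEs by treatment.

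Fourth, SAP 6.1 refers to a technical ADS plan that is not among the documents and might handle these onsets. That cannot be checked. A rule that decides between the fed and fasted columns should in any case be visible in the SAP.

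What the reply does not remove is the R-T case. The argument that a pre-tablet event is not an effect of the fed dose is no reason to show it as an on-treatment event of the fasted dose.

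**Conclusion.** The point holds and is minor. By the stated rule, an AE with onset between the start of the T breakfast and T intake is counted as fasted on-treatment in R-T and as Screening in T-R, and never as fed. The distortion can only make fed look better tolerated relative to fasted.

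Its size is limited: half an hour, 7 planned subjects by each route, an unknown and probably small number of events, and descriptive tables without hypothesis testing. The probabilities above rest on assumed rates and illustrate a range; they are not forecasts.

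A reader might also infer importance from the SAP's cut of more than 5% for the non-serious AE table, since one subject in 14 is 1/14 = 7.1%. That inference fails: with 14 subjects, any single non-serious AE passes the cut, whatever its timing.

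The conclusion assumes that onset times are recorded finely enough to separate breakfast from dosing (Protocol 5.2.6.2.1 asks for time of onset) and that the ADS plan contains no further rule.

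**What to change.** In SAP 6.1, use the option in Protocol 7.3.4 to define a separate pre-dose interval in period 2, from Day 1 admission to drug intake, and apply it in both sequences. The period-1 on-treatment phase then ends at that admission. Tabulate AEs with onset in the interval separately and not as on-treatment under the previous condition, and state which totals include them. In the AE listing, flag onsets between the start of breakfast and T intake in both periods; the nominal -0:30 h can serve if the actual meal start is not recorded. Leave the start of the fed phase at tablet intake.

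The cost is some SAP wording, one derivation, and one extra column or footnote. It is a small refinement of the protocol's intake-to-intake rule, so it should be declared in SAP Section 4, which at present reports no change from the planned analysis. With the nominal meal time, no new meal data are needed.
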